7.2.3 Anticoagulation Medications

Subjects must receive appropriate anticoagulation and other therapy according to standard hospital practice. Either unfractionated heparin or bivalirudin may be used for procedural anticoagulation, as per the discretion of the investigator. Subjects having been treated with low molecular weight heparin (LMWH) prior to the procedure should receive their last dose more than 8 hours prior to the index procedure, and then be anticoagulated during the procedure with either unfractionated heparin or bivalirudin. LMWH and fondaparinux are not permitted as procedural anticoagulants in this protocol.

Use of glycoprotein IIb/IIIa inhibitors will be at the discretion of the investigator for stable patients. Patients with biomarker positive acute coronary syndromes in whom procedural anticoagulation is achieved with unfractionated heparin should receive a procedural glycoprotein IIb/IIIa inhibitor dosed per standard of care. Glycoprotein IIb/IIIa inhibitors should not routinely be used in bivalirudin anticoagulated patients unless 1) the patient had an acute coronary syndrome and did not receive recommended pre-loading with a P2Y12 receptor inhibitor (and in whom cangrelor is not used during the PCI); and/or 2) refractory ischemic and/or thrombotic complications develop during the procedure.

7.2.4 Statin Therapy

In the absence of absolute contraindications to statin use (e.g. severe allergy with prior use), it is strongly recommended to preload with statins 12 hours prior to the procedure regardless of LDL level and history of prior or current statin use. Recommended statin loading dose regimens include atorvastatin 80 mg or rosuvastatin 40 mg.

7.3 Index Procedure

7.3.1 Baseline (Pre-Procedure) Angiography

Baseline angiography of the target vessel(s) will be completed as per the Angiographic Core Laboratory Protocol.

7.3.2 Imaging Guidance Document

The Imaging Guidance Document will provide specific details and instructions from the angiographic core laboratory regarding vessel sizing. This document will be separate from the protocol.

7.3.3 Treatment Rules of the Target Lesion(s)

Please see **Protocol Summary**, Treatment Strategy, for details of the treatment rules of target lesion(s).

7.3.4 Treatment Rules of Unplanned Non-Target Lesion(s)

In situations where treatment of a planned target lesion revealed additional lesion(s), the additional lesion(s) may be treated. These lesions are considered unplanned lesions. If the lesion meets enrollment criteria both before and after pre-dilatation, the lesion must be treated with the assigned device and will be considered as an unplanned target lesion. If the lesion does not meet the enrollment criteria (either before or after pre-dilatation), the lesion must be treated with XIENCE and will be considered as an unplanned non-target lesion.

7.3.5 Bailout Stenting or Alternative Procedures

Bailout procedures may be performed if the subject experiences:

- Dissection requiring intervention
- Occlusive complication as evidenced by a decrease in target vessel flow
- Chest pain or ischemic changes measured by ECG that do not respond to repeat balloon inflations, medical therapy or lytic agents
- Unplanned additional device is required to cover the target lesion

During randomization, if a bailout device is required for a target lesion (e.g., for edge dissection), the same device as the implanted device must be used. Overlap of the bailout stent/scaffold with the implanted stent/scaffold should be 1-2 mm. Gaps should be avoided.

- Use Absorb BVS if target lesion is treated with Absorb BVS.
- Use XIENCE if target lesion is treated with XIENCE.
- If a bailout with an Absorb BVS device cannot be delivered to the site of the lesion, the device should be carefully withdrawn and a XIENCE used.
- If an appropriate size Absorb BVS is not available XIENCE can be used.

IMPORTANT: It is required that the bailout device be placed so that there is no visible gap between the Absorb BVS and the bailout device. In such a case, at least 1 mm (minimum) to 2 mm (maximum) overlap is required.

IMPORTANT: In the rare event of acute occlusion following Absorb BVS placement and an additional drug-eluting stent is required for treatment, the bailout device should be XIENCE and deployed within the Absorb BVS such that the Absorb BVS is completely covered by the bailout device if this is believed to be in the best interest of the patient.

Although a bailout procedure is not considered a major adverse cardiac event (MACE) unless the subject sustains death, emergent CABG, PCI or MI, such procedures should be avoided unless required for safe subject management.

7.3.6 Final (Post-procedure) Angiography

Angiographic imaging will also be performed after the Absorb BVS or XIENCE stent deployment. Physicians should follow accepted hospital imaging practice to ensure good apposition of the Absorb BVS or XIENCE to the vessel wall. For angiographic imaging, post-implantation images should be captured the same orthogonal views that were used for the pre-procedure images (after the guidewire has been withdrawn). Intracoronary nitroglycerine should be re-administered before final angiography. If nitroglycerine is not available, intravenous nitroprusside or intravenous calcium channel blocker may be used per physician discretion.

7.3.7 Final (Post-procedure) IVUS and OCT

IVUS and OCT may be performed post-procedure per site standard of care. If stent or scaffold under-expansion or substantial malapposition is seen and post-dilatation required, a non-compliant balloon should be used. Do not dilate the Absorb BVS beyond the dilatation limit which is 0.5 mm above the nominal diameter. Repeat angiography in orthogonal views must be performed after any additional inflations.

7.4 Post-procedure

7.4.1 Post-procedure Information to be Recorded

The following information needs to be obtained between 12 hours following the index procedure and hospital discharge (in-hospital stay is considered to be a maximum of 7 days following the index procedure).

Between 12 hours post-procedure and discharge

- Date of discharge
- Antiplatelet medications
- Chronic concomitant medications
- Adverse Events, if any

7.4.2 Post-procedure Laboratory and Clinical Tests

The following laboratory assessments need to be obtained between post-index procedure and hospital discharge. Hospital discharge cannot occur prior to 16 hours to ensure complete post-procedure cardiac enzyme collection.

IMPORTANT: These tests must be performed whether or not they are considered part of the Investigator's standard of clinical practice.

Post-procedure and discharge

- A 12-lead ECG must be obtained within 24 hours post procedure.

- Both Creatine kinase (CK) and Creatine kinase myocardial-band isoenzyme (CK-MB) must be obtained for ALL subjects as it will be used for cardiac assessment of subjects post-index procedure
 - First post-procedure CK and CK-MB draw at 6 to 12 hours post-procedure.
 - Second post-procedure CK and CK-MB draw at 18-24 hours post-procedure, or at the time of discharge as long as discharge is at or after 16 hours post-procedure**.
 - If either of the post-procedure CK-MB levels are $\geq 5x$ ULN, serial CK and CK-MB levels must be drawn until they are falling.

** For subjects discharged prior to 16 hours, the subject will have to return to the enrolling institution for their second biomarker draw.

Alternatively, a visiting nurse may be sent to the patient's home to collect the blood sample. CK and CK-MB levels are required at all time points. Troponins are required pre-procedure and from the arterial sheath prior to first balloon inflation during the procedure in patients with acute coronary syndromes. All troponin, CK and CK-MB levels collected at any time points pre-procedure, during the procedure and post-procedure, should also be documented in the electronic case report forms.

For subjects having staged procedures, the post-procedure cardiac enzyme and 12-lead ECG assessment for the original index procedure must be repeated following the staged procedure in the same manner as done for the original index procedure.

7.4.3 Assessment of perception bias.

Patients' perception as to whether they received the control or test device may affect the rate of angina. As described in section 4.5.2, comprehensive efforts will be undertaken to maintain patient blinding. Nonetheless, for a variety of reasons patients may develop a belief as to which device they received, even if the blind is maintained.

To assess any potential perception bias on the secondary endpoint of percentage of patients who experienced angina within 1 year, information will be collected in a brief patient perception assessment questionnaire administered by the research coordinator post-procedure in the hospital prior to discharge (≥ 4 hours to ≤ 7 days after the procedure) and at 1 year. Subjects will be asked for their perception of what treatment they believe they might have received, and the basis of this perception. The following question(s) will be asked:

1. Do you think you know which treatment you have received?
 - a. Yes.
 - b. No.

If answered "Yes" to Question #1, then answer the following questions. If answered "No" to Question #1, do not answer the following questions.

2. Which treatment do you think you have received?
 - a. Standard metal stent.
 - b. Temporary dissolving stent.
3. Are you certain?
 - a. Yes.

- b. No.
- 4. Why do you think you know?
 - a. I was told by /overheard the doctor who did the procedure.
 - b. I was told by/overheard another person in the procedure room/cath lab.
 - c. I was told by/overheard another person in the hospital before discharge.
 - d. I was told by/overheard a family member or friend who was told.
 - e. I believe so because I am feeling better.
 - f. I believe so because I am not feeling better.
 - g. Other (write in).

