APPENDIX II: DEFINITIONS

Please refer to **Appendix II** of ABSORB III Protocol ([REDACTED], March 14, 2017) for complete list of definitions. New or updated definitions are listed below:

MYOCARDIAL INFARCTION (MI)

Protocol MI Definition: Periprocedural MI definition is modified from Moussa ID, Klein LW, Shah B, Mehran R, Mack MJ, Brilakis ES, Reilly JP, Zoghbi G, Holper E, Stone GW. Consideration of a new definition of clinically relevant myocardial infarction after coronary revascularization: an expert consensus document from the Society for Cardiovascular Angiography and Interventions (SCAI). J Am Coll Cardiol. 2013 Oct 22;62(17):1563-70.

This definition will be used for the primary analysis of ABSORB IV and secondary analysis of ABSORB III.

Classification	Biomarker Criteria	Additional Criteria
Periprocedural – patients with a) stable CAD, or b) silent ischemia, or c) acute coronary syndromes with at least 2 baseline troponin values which remained <ULN, or d) acute coronary syndromes in whom the troponin and/or CK-MB levels were elevated but all returned to <ULN prior to the procedure	Absolute CK-MB rises within 48 hours of the procedure to > 5 x ULN for post-PCI or CK-MB > 10 x ULN for post-CABG	Baseline value* < ULN; see also **
Periprocedural – patients with stable CAD and elevated baseline CK-MB, or acute coronary syndromes in whom at least 2 baseline troponin and CK-MB values were drawn and the most recent troponin and CK-MB values were less than the preceding measures by >25%	Absolute incremental CK-MB rise within 48 hours of the procedure from the most recent CK-MB level by > 5 x ULN for post-PCI or > 10 x ULN for post-CABG	

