4. At least two post-procedure draws required: 1) 6-12 hours post-procedure; 2) 18-24 hours post-procedure or at the time of discharge as long as discharge is at or after 16 hours post-procedure (for hospitals required to discharge stable subjects prior to 16 hours, the subject may be discharged but will have to return to the enrolling institution for their second biomarker draw). If either of the post-procedure CK-MB levels are ≥ 5 x ULN, serial CK and CK-MB levels must be drawn until they are falling.

5. Pre-procedure ECG preferred to be done within 24 hours. Post-procedure ECG must be done within 24 hours post-index procedure.
6. Refer to body of the protocol for details regarding pre-procedure antiplatelet loading requirements. Post-procedure: prasugrel 5 or 10 mg daily, clopidogrel a minimum of 75 mg daily or ticagrelor 90 mg twice daily, must be given for a minimum of 12 months, and Aspirin ≥ 75 mg to ≤ 100 mg daily must be taken through 5 years follow up (potentially up to 10 years follow-up) during the study, and should continue to be taken indefinitely. If a subject develops hypersensitivity to clopidogrel, prasugrel or ticagrelor, subject may be switched to ticlopidine at a dose in accordance with standard hospital practice.
7. For unscheduled visits for suspected ischemic cardiac events, sites should make reasonable efforts to obtain cardiac enzymes (Troponin I or T), CK and CK-MB, and/or ECG if the site is aware of the visit at the time of its occurrence. In all other scenarios (i.e., site does not become aware until after the fact), no protocol deviation will be issued if Troponin I or T, CK and CK-MB, and/or ECG were not obtained at the time of the unscheduled visit.
8. Baseline (prior to pre-dilatation) and final (after stenting/post dilatation) angiogram must be obtained and sent to the core laboratory.
9. Every effort should be made to have subjects complete all patient reported outcomes questionnaires (EQ-5D and SAQ-7) prior to the procedure. However, in situations where this is absolutely not possible, subjects may complete them post-procedure, prior to discharge. Subjects who complete their questionnaires post-procedure should base their responses on their condition prior to the procedure.
10. All registered subjects may complete PRO (EQ-5D and SAQ-7) at 30, 180 days, and at 1, 3 and 5 years.

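### In ABSORB IV the trigger for further CK-MB sampling equals the periprocedural MI cut-off for normal-baseline subjects, so a crossing after the second draw may not be captured in 30-day TLF

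*Protocol*

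**What the plan says.** **Sampling, ABSORB IV.** Protocol section 7.4.2 asks for a "First post-procedure CK and CK-MB draw at 6 to 12 hours post-procedure" and a "Second post-procedure CK and CK-MB draw at 18-24 hours post-procedure, or at the time of discharge", the latter allowed from 16 h. For anyone who leaves earlier, "the subject will have to return to the enrolling institution for their second biomarker draw", or a nurse may take it at home. Appendix III note 4 agrees: "At least two post-procedure draws required". Sampling continues beyond the second draw only if a value is at least 5 times "ULN, serial CK and CK-MB levels must be drawn until they are falling". The same trigger stands in the ABSORB IV Protocol Summary (Cardiac Biomarker Collection), in section 7.4.2 and in Appendix III note 4.

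**Endpoint, ABSORB IV.** Appendix II defines periprocedural MI for subjects with normal or normalised baseline values by "Absolute CK-MB rises within 48 hours of the procedure to > 5 x ULN for post-PCI". For stable CAD with elevated CK-MB at baseline, and for ACS with falling values, it is an "Absolute incremental CK-MB rise within 48 hours of the procedure from the most recent CK-MB level by > 5 x ULN for post-PCI". Where baseline CK-MB is elevated and not shown to be stable or falling, the same increment plus ECG and clinical signs is needed. In stable CAD with a baseline and a post-procedure CK-MB available, adjudication rests on those values alone. Troponin is not used for periprocedural MI.

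**ABSORB III, same protocol number.** The cut-off after PCI with normal baseline is also above 5x ULN (ABSORB III Appendix II), but further sampling starts at 3x ULN (Protocol Summary, section 7.4.2, Appendix III note 3).

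**Use of the endpoint.** Target-vessel MI is a component of 30-day TLF (ABSORB IV section 5.1), tested for non-inferiority with a 2.9-point margin at one-sided 0.025 (SAP section 1.5.1). TLF through 5 years is planned on 4600 subjects from both trials (ABSORB IV section 5.3), and SAP section 2.1 plans summaries for the same pooled population.

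**The concern.** A rule for continued sampling helps to find events only if it starts below the level that defines the event. For normal-baseline subjects in ABSORB IV it starts at that level. It therefore follows up subjects who already meet the MI criterion (or sit at exactly 5x) and requires nothing of those who are approaching it.

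At stake is the completeness of one component of the primary endpoint. In a non-inferiority comparison of absolute risks, losing the same fraction of events in both arms pulls the observed difference towards zero, and so towards the conclusion the trial hopes to reach. The pooled analyses would also combine two trials in which periprocedural MI was sought under different sampling rules.

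**Working it through.** **1. Lead of the trigger over the cut-off** (cut-off minus trigger, in multiples of ULN)

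- ABSORB III, normal baseline: 5 - 3 = 2.
- ABSORB IV, normal or normalised baseline: 5 - 5 = 0.
- ABSORB IV, baseline elevated at b: MI needs a value above b + 5, so the lead is (b + 5) - 5 = b. At b = 1.5 the MI level is 6.5 and the lead 1.5; at b = 2 they are 7 and 2.

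The gap is therefore confined to normal or normalised baselines.

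**2. Part of the 48 h window with no required sample** when both draws are below 5x

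- Second draw at 24 h: 48 - 24 = 24 h.
- Second draw at 18 h: 48 - 18 = 30 h.
- Second draw at discharge at 16 h: 48 - 16 = 32 h.

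Example: a subject at 2x at 8 h and 4.6x at 16 h needs no further sample for 32 h, although the value has more than doubled.

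**3. Other routes to detection.** Troponin cannot make the diagnosis. The spontaneous MI category applies only later than 48 h after a procedure. Enzymes at unscheduled visits (section 7.6) presuppose a suspected ischemic event and are asked for as a reasonable effort. A silent late crossing has no required route to detection.

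**4. The plan's own power figure.** SAP section 1.5.1 gives about 92% power with n = 1287 per arm, margin m = 2.9 points and one-sided 0.025. The assumed event rates are blacked out, so the figure cannot be reproduced directly. The Farrington-Manning power is

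Φ[(m - d - 1.96·s0) / s1],

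where d is the difference in rates, s1 = √{[pT(1-pT) + pC(1-pC)]/n}, and s0 is the same expression at the rates fitted under a difference of m. With equal rates of 5.0%, s0 = 0.00887 and s1 = 0.00859, so Φ(1.352) = 91.2%. A power of 92% corresponds to equal rates of about 4.7-4.9%. A control rate of 5.0% is thus a reasonable illustration, but it is an assumption.

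**5. Effect of an equal proportional loss.** If a fraction f of TLF events is missed in each arm, the observed rates are (1-f)·pT and (1-f)·pC, and the observed difference is (1-f)·(pT - pC). Take pC = 5.0% and pT = 7.9%, so that the true difference equals the margin:

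| f | Events missed, control (64.35·f) | Events missed, Absorb (101.67·f) | Observed difference (points) | Chance of declaring non-inferiority |
|---|---|---|---|---|
| 0 | 0 | 0 | 2.90 | 2.5% |
| 2% | 1.3 | 2.0 | 2.84 | 2.9% |
| 5% | 3.2 | 5.1 | 2.76 | 3.5% |
| 10% | 6.4 | 10.2 | 2.61 | 5.0% |

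Here 64.35 = 1287 × 0.050 and 101.67 = 1287 × 0.079. For f = 10%: s0 = 0.00923, s1 = 0.00920, and (0.0290 - 0.0261 - 1.96 × 0.00923)/0.00920 = -1.65, giving 5.0%. With control rates of 4.5-6.0%, the 10% row gives 4.8-5.1%.

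The values of f are illustrative; no document gives a CK-MB distribution from which f could be estimated.

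**The case against.** - **The second draw protects most subjects.** A first value below 5x is always followed by a second required draw, including after early discharge. A reader might infer that subjects below 5x are never resampled. The text does not support that: later draws are not required, but nothing bars them, and all values collected are to be recorded. Only a first crossing after the second draw and before 48 h is exposed.
- **A reader might infer that MIs are in fact missed, perhaps more in one arm.** The documents show only that they could be. The rule is the same in both arms, and nothing supports a particular frequency or imbalance.
- **The trigger is not the MI threshold for everyone.** ABSORB IV admits NSTEMI and recent STEMI, and with elevated baseline CK-MB the 5x trigger does lead the MI level. It is also incomplete to say that only the trigger changed between the trials: the elevated-baseline rules changed too. The comparison with ABSORB III holds for the normal-baseline PCI cut-off.
- **Other definitions help in part.** Modified WHO and Universal MI are planned secondary analyses. Under the WHO definition, the subject at 4.6x would count if CK were at least twice ULN. The visible text does not say that 30-day TLF is recomputed on these definitions, so this mitigates the gap without closing it. Applying the ABSORB IV definition secondarily to ABSORB III aligns definitions, not sampling.
- **Equal loss does not always bias.** Losing the same number of events per arm, rather than the same proportion, leaves the difference unchanged.

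These objections narrow the point. They leave standing that required extra sampling cannot reveal a new MI in normal-baseline subjects.

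**Conclusion.** The point holds for subjects with normal or normalised baseline CK-MB. In them the trigger gives no lead over the MI cut-off, and a value that is rising but below 5x at the second draw leaves 24-32 h of the MI window without a required sample. Late crossings may be absent from 30-day TLF, and the pooled 4600-subject analyses rest on two sampling rules.

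The size is unknown and may be small. The shift from 2.5% to 2.9-5.0% assumes a 5.0% control rate, a true difference at the margin and a loss of 2-10% of all TLF events, equal in proportion across arms. The documents establish none of these. This is a gap in endpoint ascertainment that should be closed and quantified; it does not show that the primary result is biased.

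**What to change.** 1. Reconcile the trigger in the ABSORB IV Protocol Summary, section 7.4.2 and Appendix III note 4 with the MI definition in Appendix II and with the ABSORB III rule, so that required sampling continues below the endpoint cut-off when the last value is not falling. The cost is a wording change and one or two extra blood samples in a few subjects. It helps only subjects not yet treated.
2. From CK-MB data already recorded, tabulate by arm the normal-baseline subjects whose last value was 3-5x ULN and not lower than the previous draw. Repeat the 30-day TLF non-inferiority test counting those without a TLF event as target-vessel MI. Label it a worst-case bound for that band, since not all of them will have crossed 5x. The cost is one table and one sensitivity analysis, with no new data. If very few subjects qualify, the table settles the matter. If a blacked-out part of the SAP already provides this, a reference to it is enough.
3. State beside the pooled 4600-subject results that the two trials used different triggers for continued CK-MB sampling.

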5.2 ABSORB IV Major Secondary Endpoint

- **TLF through 1-year, tested for non-inferiority against the control**
- **ABSORB IV Angina Powered Secondary Endpoint:** The percentage of patients who experienced angina within 1 year, tested first for non-inferiority with reflex to superiority against the control.
 - Angina is defined as any angina or angina equivalent symptoms determined by the physician and/or research coordinator after interview of the patient, and as adjudicated by a clinical events committee (CEC).

- This analysis will exclude angina or angina equivalent symptoms that occurred following the index procedure through hospital discharge or 7 days, whichever occurs first.
- This analysis will consist of ~2600 subjects in ABSORB IV.

5.3 *Additional Secondary Endpoint(s)*

In ABSORB IV the following clinical secondary endpoints will be analyzed for all the ~2600 subjects.

- **Acute Success:** (Combined Clinical/Angiographic Endpoint)
 - Device success (Lesion level analysis)
 - Procedural success (Subject level analysis)
- **Clinical Endpoint** in hospital and at each follow-up point (30, 90, 180, 270 days; 1, 2, 3, 4, 5 years).
 - **Component**
 - Death (Cardiac, Vascular, Non-cardiovascular)
 - Myocardial Infarction
 - Attributable to target vessel (TV-MI)
 - Not attributable to target vessel (NTV-MI)
 - Target Lesion Revascularization (TLR)
 - Ischemia driven TLR (ID-TLR)
 - Non ID TLR (NID-TLR)
 - Target Vessel Revascularization (TVR,)
 - ID TVR
 - Non ID TVR
 - All coronary revascularization
 - **Composite Endpoints**
 - Death/All MI
 - Cardiac Death/All MI

- Cardiac Death/TV-MI/ID-TLR (TLF)
- Cardiac Death/All MI/ID-TLR (MACE)
- Cardiac Death/All MI/ID-TLR/ID-TVR, non TL (Target Vessel Failure, TVF)
- Death/All MI/All revascularization
- **Scaffold-Thrombosis / Stent Thrombosis (per ARC definition)**
 - Timing (acute, sub-acute, late and very late)
 - Evidence (Definite and Probable)
- Rehospitalization
 - Coronary artery disease related
 - Cardiovascular, non-CAD related
 - Non-cardiovascular related
- Repeat coronary arteriography
- TLF through 5 years based on 4600 subjects (2000 primary analysis subjects of ABSORB III and 2600 subjects of ABSORB IV)

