7.5 Clinical Follow-up for All Subjects

Please see **Protocol Summary** for clinical follow-up schedule and PRO follow-up assessments.

Registered subjects must be clinically followed even if no assigned device is implanted. Clinical follow-up visits must be conducted by a blinded physician, research coordinator, Nurse Practitioner or Physician Assistant who has been trained to the protocol.

For subjects having staged procedures, the follow-up period is considered as having begun upon completion of the original index procedure.

To assess any potential perception bias on the secondary endpoint of percentage of patients who experienced angina within 1 year, information will be collected in a brief patient perception assessment questionnaire administered by the research coordinator post-procedure in the hospital prior to discharge (≥ 4 hours to ≤ 7 days after the procedure) and at 1 year.

The PRO questionnaires will be mailed to the subject for completion or can be completed during the phone or office visit. If questionnaires are mailed to the subjects, the subjects must mail the questionnaires back to the clinical site.

The following information will be collected at each of the time points:

- Any adverse events (including re-hospitalizations)*, repeat coronary angiography, details regarding angina, medications, laboratory tests and 12-lead ECGs, if performed;
- Any angina events
 - If the subject experiences any symptoms of abnormal chest/arm/neck/jaw discomfort or pain, including angina-equivalent or atypical angina pain/sensation, data will be solicited and recorded regarding angina and angina-equivalent symptoms, including the quality, frequency and severity of discomfort/pain, to allow the CEC to adjudicate the symptoms as to angina/angina-equivalent vs. non-angina. This information will be collected by the research coordinator using a standard script. A blinded cardiologist will review the information collected by the research coordinator, provide a diagnosis and sign-off on his/her diagnosis.
- Any repeat coronary angiography and results of such, if applicable;
- Details of any subsequent coronary interventions (e.g., repeat PCI or CABG);
- Use and compliance of medications per clinical investigation plan;
- Use and changes in concomitant cardiovascular medications.

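### ABSORB IV gives the research coordinator role both the patient-perception questionnaire and the angina interview, and no visible text separates the two tasks, so the procedure can unblind the angina interviewer

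*Protocol*

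**What the plan says.** **Perception questionnaire.** ABSORB IV section 7.4.3 describes a "patient perception assessment questionnaire administered by the research coordinator post-procedure in the hospital prior to discharge", given between 4 hours and 7 days after the procedure and again at 1 year. Section 7.5 repeats this. Question 1 asks whether patients think they know their treatment. Only those who say yes go on to "Which treatment do you think you have received" (metal or dissolving stent), whether they are certain, and why. Four of the seven listed reasons are being told or overhearing, the first being "I was told by /overheard the doctor who did the procedure".

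**Angina data.** Section 7.5 says of the symptom details (quality, frequency, severity): "This information will be collected by the research coordinator using a standard script". The coordinator is also part of the endpoint definition in section 5.2: "Angina is defined as any angina or angina equivalent symptoms determined by the physician and/or research coordinator after interview of the patient", followed by adjudication by the clinical events committee (CEC).

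**Blinding and review.** Section 7.5 also states: "Clinical follow-up visits must be conducted by a blinded physician, research coordinator, Nurse Practitioner or Physician Assistant who has been trained to the protocol". After the interview, "A blinded cardiologist will review the information collected by the research coordinator, provide a diagnosis and sign-off on his/her diagnosis". The CEC then classifies the symptoms (section 9.1).

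**Not visible.** ABSORB IV section 4.4.2 (Blinding) and SAP section 1.6.2 (Blinding) are redacted.

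**The concern.** Section 7.5 needs a coordinator who does not know the device. Section 7.4.3 has the same role ask patients about the device and how they learned of it. A patient who answers that they are certain because the operator told them has in effect disclosed the allocation to the person asking.

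Angina within 1 year is a powered secondary endpoint, tested for non-inferiority with reflex to superiority, and it rests on symptoms drawn out in conversation. If the interviewer knows or believes they know the device, probing and recording can differ between arms. A tool meant to measure perception bias in patients could then introduce assessor bias into the record that is later adjudicated.

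**Working it through.** **1. Timing.** The angina analysis excludes symptoms up to discharge or 7 days, whichever is first (section 5.2). The first questionnaire falls in hospital, at most 7 days after the procedure. The scheduled contacts that feed the endpoint are at 30, 90, 180 and 270 days and 1 year (Protocol Summary). The first questionnaire therefore precedes almost all angina interviews that count. At 1 year both instruments are due, and no visible text says which comes first.

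**2. Overlap.** Sections 7.4.3 and 7.5 each name the research coordinator for their task. Neither says that a different person must do the other task, or that the answers are kept from the interviewer.

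**3. The plan's own figure, for scale.** SAP section 1.5.2.2 gives 1235 per arm, a 7-point margin, one-sided alpha of 2.5% and about 99% power for non-inferiority on angina. The assumed rates are redacted. A Farrington–Manning calculation with equal rates gives 99.7% at 16%, 99.1% at 20%, 98.0% at 25% and 97.3% at 27.9%. The stated power is compatible with rates in this range but cannot be strictly reproduced. The concern does not depend on it.

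**4. Net bias (illustrative).** Let f be the share of patients in each arm who disclose a belief and a the probability that the belief is correct. Let recorded angina fall by 10 points in those believed to have Absorb.
- Absorb arm: recorded rate falls by 10 × f × a.
- XIENCE arm: recorded rate falls by 10 × f × (1 − a).
- Net bias towards Absorb: f × 10 × (2a − 1).

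| Accuracy a | f = 10% | f = 20% |
|---|---|---|
| 50% | 0 | 0 |
| 75% | 0.5 point | 1 point |
| 100% | 1 point | 2 points |

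The values of f, a and the 10-point shift are assumptions; the documents give none of them.

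**5. Effect on the superiority test.** The standard error is √(2p(1 − p)/1235). The range of p, 16–28%, covers the rates in the retrospective comparisons in ABSORB IV sections 2.2 and 12.2. With equal true rates, the chance of a false finding in favour of Absorb is P(Z > 1.96 − bias/SE).

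| p | SE (points) | No bias | 0.5 point | 1 point | 2 points |
|---|---|---|---|---|---|
| 16% | 1.48 | 2.5% | 5.2% | 10.0% | 27.3% |
| 20% | 1.61 | 2.5% | 5.0% | 9.0% | 23.7% |
| 28% | 1.81 | 2.5% | 4.6% | 8.0% | 19.7% |

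A version that lowers the recorded rate in the Absorb arm when computing the variance gives 20–29% for 2 points.

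**6. Effect on non-inferiority.** If Absorb were truly 7 points worse, masking 1 point would raise the false non-inferiority rate from 2.5% to about 8–9%, and masking 2 points to about 19–25%. As shares of the margin, 1/7 = 14% and 2/7 = 29%.

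**The case against.** **Redaction.** The sections where one would expect rules on who is blinded and who holds which data are blacked out. A reader might infer that the plan has no separation of the two tasks. The documents do not support that, because the separation may sit in the redacted text. What stands is that 7.4.3 and 7.5 are legible operating instructions that name the same role without qualification.

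**A role is not a person.** A reader might also infer that one individual does both tasks for each patient. The text names only a role, and the rule on blinded follow-up staff can be read as barring a coordinator who has become unblinded. But it also allows one person to do both, and no visible step detects or handles unblinding.

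**The form asks for belief.** It does not ask every patient which device was implanted and who told them. Questions 2 to 4 go only to those who think they know. Two of the listed reasons are feeling better or not feeling better, which are guesses and reveal nothing about allocation. This is why the illustration must allow for accuracy: wrong beliefs cancel right ones.

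**Safeguards.** The script, the blinded cardiologist, CEC adjudication, adverse events taken from medical records, and the self-administered SAQ-7 all reduce the risk, so the coordinator is not the only source. Even so, the reviewers of an interview cannot recover symptoms that were not elicited or were written down as milder.

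**Patients may volunteer their device anyway.** True, but here the procedure asks for it.

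**Conclusion.** The concern holds as a design weakness in the visible text. The same role is told to ask about perceived allocation and to collect the data for a subjective powered endpoint, with no visible separation and no fixed order at 1 year. The documents show that unblinding can happen. They do not show that it did, or that any angina result would be biased.

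The size is unknown. Under the stated assumptions (10–20% disclose, a 10-point shift, equal disclosure and accuracy in both arms), the net bias runs from zero at 50% accuracy, through 0.5–1 point at 75% (false superiority about 5–10%), to 1–2 points at 100% (about 8–27%). The top of that range needs every disclosed belief to be correct, and should not be read as the expected effect. The structural point stands without these figures. The change is worth making because it is cheap, unless the redacted sections already provide for it; in that case 7.4.3 and 7.5 should say so.

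**What to change.** In 7.4.3 and 7.5, replace administration by the research coordinator with the following:
- The patient completes the perception form without the angina interviewer: sealed on paper in hospital, and by mail or direct electronic entry when the 1-year contact is by telephone, which the Protocol Summary allows.
- The answers sit in an eCRF form hidden from angina interviewers, the blinded cardiologist and the CEC.
- At 1 year the form is given only after the angina script has been completed and signed off.

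**Cost.** A short amendment and a change to eCRF access rights, with no extra visit or staff. Self-administered and mailed questionnaires are already part of the trial. Somewhat more answers will be missing, and patients may still volunteer their device in an interview, so the change reduces the risk without removing it. It cannot repair interviews already done. For those, a sensitivity analysis leaving out patients who report being certain because they were told would show how far the result depends on them.
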